10.2 KEY SECONDARY EFFICACY PARAMETERS

The key secondary efficacy parameter will be the change from baseline in MADRS total score at 1 day after first dose of randomized IP. The key secondary efficacy parameter will be analyzed in the same MMRM model for the primary efficacy parameter. The treatment differences for rapastinel 450 mg versus placebo and rapastinel 900 mg versus placebo will be estimated and reported along with the corresponding 95% CIs and p-values.

[figure not shown]
Let H_1 and H_2 represent the treatment effect comparing rapastinel 450 mg versus placebo and rapastinel 900 mg versus placebo in regards to the primary efficacy parameter of change from baseline in MADRS total score at end of treatment (end of Week 6), respectively; and let H_3 and H_4 represent the treatment effect comparing rapastinel 450 mg versus placebo and rapastinel 900 mg versus placebo in regards to the secondary efficacy parameter of change from baseline in MADRS total score at 1 day after first dose of treatment. The graphical procedure displayed in Figure 10-1 will be employed to control the overall familywise error rate at $\alpha = 0.049$.

[figure not shown]
Figure 10-1

Graphical Testing Procedure

Specifically, H_1 and H_2 will be tested at $\alpha = 0.0245$ separately. If H_1 is rejected, H_3 will then be tested at $\alpha = 0.0245$. If H_2 is rejected, H_4 will then be tested at $\alpha = 0.0245$. If H_3 is rejected but H_2 is not rejected, H_2 will be further tested at $\alpha = 0.049$. If H_2 is rejected at $\alpha = 0.049$, H_4 will be further tested at $\alpha = 0.049$. Similarly, if H_4 is rejected but H_1 is not rejected, H_1 will be further tested at $\alpha = 0.049$. If H_1 is rejected at $\alpha = 0.049$, H_3 will be further tested at $\alpha = 0.049$.

[REDACTED]

[REDACTED]

[REDACTED]

[REDACTED].

11.1 ADVERSE EVENTS

[figure not shown]
Adverse events will be coded using the *Medical Dictionary for Regulatory Activities* and summarized separately for the DBTP and SFUP.

[figure not shown]
An AE (classified by preferred term) will be considered a treatment-emergent adverse event (TEAE) during the DBTP if it was present after the first dose of IP, or was present before the date of the first dose of IP and increased in severity or became serious after the first dose of IP. If more than 1 AE was reported before the first dose of IP and coded to the same preferred term, the AE with the greatest severity will be used for comparison with the AEs occurring during the DBTP or safety follow-up period. For patients who complete this study and enters the RAP-MD-33 study, an AE that occurs on or after the last day of the DBTP will not be considered as a TEAE. For patients who do not enter the RAP-MD-33 study, an AE that occurs more than 30 days after the date of the last dose of IP will not be considered as a TEAE.

[figure not shown]
The number and percentage of patients reporting TEAEs in each treatment group will be tabulated by system organ class and preferred term, and further categorized by severity and causal relationship to the IP. If more than 1 AE is coded to the same preferred term for the same patient, the patient will be counted only once for that preferred term using the greatest severity and strictest causality for the summarization by severity and causal relationship.

[figure not shown]
The incidence of common ($\geq 2\%$ of patients in any treatment group) TEAEs will be summarized by preferred term and treatment group and sorted by decreasing frequency for the test treatment.

[figure not shown]
Overall summaries of AEs will be provided on a per-patient basis for categories of all TEAEs, treatment-related TEAEs, death, Treatment-emergent serious AEs (TESAEs), and TEAEs leading to study discontinuation.

[figure not shown]

[figure not shown]

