Signed informed consent from the patient or the patient's legally authorized representative will be obtained before any study-related procedures are begun. Patients will wash out any previous ADT and/or prohibited medications during the screening period. Patients meeting the eligibility criteria at the end of Visit 2 will be randomized in a ratio of 1:1:1 to one of the three treatment arms: rapastinel 900 mg IV weekly, rapastinel 450 mg IV weekly, or placebo IV weekly. The double-blind treatment period (DBTP) starts with the first dose of study treatment. Upon completion of the DBTP, patients may be eligible to enter the extension study. Patients who do not enter the extension study will enter a 2-week safety follow-up period. Efficacy and safety assessments will be conducted at the clinic 1 day following the treatment day in the 1st week and at the ends of weeks 1, 2, 3, 4, 5 and 6 of the DBTP. Patients prematurely discontinuing from the study, regardless of cause, will be seen for a final evaluation. The schedule of evaluations for Study RAP-MD-32 is presented in [Table 4-1](#).

[figure not shown]

[figure not shown]

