16.4 MISSING SEVERITY ASSESSMENT FOR ADVERSE EVENTS

If severity is missing for an AE that started before the date of the first dose of study treatment, an intensity of mild will be assigned. If severity is missing for an AE that started on or after the date of the first dose of study treatment, an intensity of severe will be assigned. The imputed values for severity assessment will be used for the incidence summary; the values will be shown as missing in the data listings.

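### The TEAE definition admits any event present after the first dose, so pre-dose events that merely continue unchanged count as treatment-emergent

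*SAP*

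**What the plan says.** Section 11.1 of the SAP defines treatment emergence by preferred term, with two alternative conditions. An event qualifies "if it was present after the first dose of IP, or was present before the date of the first dose of IP". The second alternative reads in full "or was present before the date of the first dose of IP and increased in severity or became serious after the first dose of IP".

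Where several pre-dose events share a preferred term, "the AE with the greatest severity will be used for comparison with the AEs occurring during the DBTP or safety follow-up period".

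The section's only exclusions concern late events. For patients who enter the extension study, events on or after the last day of the double-blind period are excluded. For the others, "an AE that occurs more than 30 days after the date of the last dose of IP will not be considered as a TEAE". Nothing removes an event that was already there before dosing and did not change.

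**The concern.** A treatment-emergent rule has to separate events that are new or worse after dosing from those that were already present. The first condition asks only whether the event was present after the first dose, and an event carried over from screening at the same severity meets it.

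Carried-over events are plausible in this trial. Section 4.0 states: "Patients will wash out any previous ADT and/or prohibited medications during the screening period". A patient coming off an antidepressant may have symptoms still ongoing at the first infusion. Section 16.4 has a rule for events that started before the first dose, so the plan expects such events in the database.

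The definition feeds every TEAE output in Section 11.1: incidence by system organ class and preferred term, the breakdowns by severity and causality, the table of common events (at least 2% in any group), and the overall summaries of treatment-related events, serious events and events leading to discontinuation.

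**Working it through.** The SAP states no figure on this point that could be reproduced. The check is a logical one, followed by an illustration on assumed rates.

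**Step 1. The rule as written against a new-or-worsened rule.** For a given preferred term, let B = present before the first dose, A = present after it, W = worsened or became serious after it.

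- As written: TEAE = A or (B and W)
- New or worsened: TEAE = (A and not B) or (B and W)

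| Case | As written | New or worsened |
|---|---|---|
| Never present | no | no |
| New after dose | yes | yes |
| Before only, resolved | no | no |
| Before and after, not worse | **yes** | **no** |
| Before and after, worse | yes | yes |

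The rules differ in one row. Because the flags are set by preferred term, that row holds events that continue unchanged and also events that resolve and recur at no greater severity.

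**Step 2. The second condition is redundant.** An event that worsened after dosing was necessarily present after dosing, so W implies A. The written rule reduces to TEAE = A. Neither the worsening condition nor the choice of the worst pre-dose severity as comparator can change any classification.

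**Step 3. Comparison with the data-handling sections.**

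- Section 16.4 splits events by start date: a missing severity is set to mild for events starting before the first-dose date and to severe for events starting on or after it. That split suits a worsening comparison.
- Section 16.5 imputes missing causality only for events that started on or after the first-dose date. A carried-over event with missing causality would enter the TEAE-by-relationship table with no category assigned.
- Section 16.6 imputes adverse event start dates around the first dose and gives no imputation for stop dates. Under the rule as written, a pre-dose event's status turns on whether it was still ongoing, which depends on its stop date.

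These sections are built on onset, whereas the definition is built on presence.

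**Step 4. Illustration, all TEAEs.** Assumed, not from the SAP: true incidence p = 50% on drug and 40% on placebo; a fraction c of patients in each arm with an unchanged pre-dose event, independent of true TEAEs. Reported incidence = 1 − (1 − p)(1 − c).

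| c | Drug | Placebo | Difference (points) |
|---|---|---|---|
| 0 | 50% | 40% | 10 |
| 5% | 1 − 0.50 × 0.95 = 52.5% | 1 − 0.60 × 0.95 = 43% | 9.5 |
| 10% | 1 − 0.50 × 0.90 = 55% | 1 − 0.60 × 0.90 = 46% | 9 |
| 20% | 1 − 0.50 × 0.80 = 60% | 1 − 0.60 × 0.80 = 52% | 8 |

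**Step 5. Illustration, one preferred term.** Assumed new-onset incidence 10% on drug and 5% on placebo; same formula. Extra placebo patients = c × 0.95 × 230, with 230 per group from Section 14.0.

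| c | Drug | Placebo | Risk ratio | Extra placebo patients |
|---|---|---|---|---|
| 0 | 10% | 5% | 2.00 | 0 |
| 2% | 11.8% | 6.9% | 1.71 | 4.4 |
| 5% | 14.5% | 9.75% | 1.49 | 10.9 |
| 10% | 19% | 14.5% | 1.31 | 21.9 |
| 20% | 28% | 24% | 1.17 | 43.7 |

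**Step 6. The common-event table.** Section 11.1 says the common "TEAEs will be summarized by preferred term and treatment group and sorted by decreasing frequency for the test treatment". With 230 patients in a group, 2% is 0.02 × 230 = 4.6, so five patients with an unchanged carried-over event of one term are enough to list it.

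**The case against.** The strongest reply is that the intent is visible. The worsening condition, the pre-dose severity comparison and the onset-based rules in Sections 16.4 to 16.6 all point to a new-or-worsened definition, and an experienced programmer may well implement that. This stands as evidence of intent, and it is why the problem is best called a drafting error and not a deliberate choice. It does not rescue the text: no other section restates or corrects the definition, and two programmers could read it differently.

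The effect is also uncertain. Every rate in the illustrations is assumed. Section 4.0 admits treatment-naive patients, some with no antidepressant in the present episode, so not everyone has a washout. The SAP does not say that withdrawal symptoms occur or are recorded as adverse events. Section 11.1 plans counts and percentages and no hypothesis tests. All of this stands and limits the size of the claim.

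Two objections concern the remedy. A cut at the first-dose date would still count an event that begins earlier on the day of the first infusion. That is true, but the same date-level cut is already used in the second condition and in Sections 16.4 and 16.5. The correction would also exclude a same-term recurrence at equal severity; that is what a comparison by preferred term with the worst pre-dose severity is for.

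**Conclusion.** The concern holds. Followed literally, Section 11.1 counts pre-existing, unchanged events as treatment-emergent and makes its own worsening and comparison rules idle. That conclusion rests on the wording alone and needs no assumed rate.

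The size is unknown, because it depends on how many patients have an event ongoing at the first dose. In the illustrations, a carry-over of 5% to 20% takes 0.5 to 2 points off a 10-point difference in overall TEAE incidence. For a single term with a true risk ratio of 2.00, the same range of carry-over brings the ratio down to between 1.49 and 1.17. These figures assume equal carry-over in all arms, as randomization should give on average, and independence from true TEAEs. On those assumptions the result is inflated incidence and diluted contrasts, not a systematic tilt toward one arm. Efficacy analyses, type I error and power are untouched. The definition should be corrected because every TEAE table rests on it.

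**What to change.** In Section 11.1, replace the first condition so that it covers only events, by preferred term, that were not present before the first-dose date. Leave the second condition, the pre-dose severity comparison and the late-event exclusions as they are. This restores the function of the second condition and the comparison rule, and brings the definition into line with Sections 16.4 to 16.6. The cost is one phrase in the SAP and a check that the TEAE flag is programmed to match. No new data are needed.

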13.0 INTERIM ANALYSIS

An unblinded interim analysis will be conducted in order to identify early signs of futility. Separate Statistical Analysis Group and Data Review Committee will be established to conduct the unblinded interim analysis, review the unblinded results, and make recommendations regarding the continuation of the study. In order to maintain the scientific reliability of possible final results and guard from introducing any potential bias into the conduct of the study and/or analysis of its results, individuals in these 2 groups will not be involved in any operational aspect of the study. Additionally, to adjust for multiple comparison issues caused by having several looks at the data, the Bonferroni method will be applied to split the overall Type I Error between the interim and final analysis ($\alpha = 0.001$ and 0.049 two-sided, respectively) in order to further protect the integrity of the study. Further details of the unblinded interim analysis, in particular, its scope, the processes put in place to maintain study integrity, team structures, and responsibilities, are documented in the Data Review Committee Charter.

14.0 DETERMINATION OF SAMPLE SIZE

This study initially planned to randomize approximately 690 patients to the rapastinel 450 mg, rapastinel 900 mg, and placebo groups in a 1:1:1 ratio. The primary efficacy endpoint is the change from baseline in the MADRS total score at the end of Week 6. Assuming the SD is 10 points, within-patient correlation is 0.6, and dropout rate over 6 weeks is 20%, a sample size of 230 patients per treatment group will provide 91% power to detect a difference of 3.5 points for each rapastinel dose versus placebo at a 2-sided significance level of 4.9% originally adjusting for multiple comparisons of 2 rapastinel groups with placebo across the primary and secondary endpoints by using a graphical testing procedure.

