DBTP	double-blind treatment period
DSM-5	Diagnostic and Statistical Manual of Mental Disorders, Fifth Edition
DxV	Diagnostic Validation
ECG	electrocardiogram, electrocardiographic
eCRF	electronic case report form
ET	early termination
ICF	informed consent form
IP	investigational product
LLN	lower limit of normal
MADRS	Montgomery-Åsberg Depression Rating Scale
MDD	major depressive disorder
MedDRA	Medical Dictionary for Regulatory Activities
mITT	modified intent to treat

MMRM	mixed-effects model for repeated measures
PCS	potentially clinically significant
PID	patient identification
PK	pharmacokinetic
QTc	QT interval corrected for heart rate
QTcB	QT interval corrected for heart rate using the Bazett formula ($QTcB = QT/(RR)^{1/2}$)
QTcF	QT interval corrected for heart rate using the Fridericia formula ($QTcF = QT/(RR)^{2/3}$)
SAE	serious adverse event
SAP	statistical analysis plan
SE	Standard Error
SFUP	Safety Follow-up Period
SI	Le Système International d'Unités (International System of Units)
TEAE	treatment-emergent adverse event
UDS	urine drug screen
ULN	upper limit of normal

3.0

HISTORY OF CHANGE

Section No.	Section Name	Description
General Notes		
The following changes are implemented in the statistical sections of protocol amendment 1 (dated May 22, 2019):
 
1. The gatekeeping serial testing procedure was replaced by the graphical testing procedure to adjust for multiple comparisons in the primary and secondary efficacy parameters for both rapastinel doses versus placebo. The section of “interim analysis” was added based on the proposal agreed by the FDA (response dated dd May 2019).2. The section of “determination of sample size” was revised to reflect the associated changes in the significance level and associated power for the final primary efficacy analyses due to the addition of interim analysis. 
These changes are now implemented in Sections 10.2 (KEY SECONDARY EFFICACY PARAMETERS), 13.0 (INTERIM ANALYSIS) and 14.0 (DETERMINATION OF SAMPLE SIZE) of this SAP amendment.
 
In addition, other revisions were documented in this history of change and implemented in this SAP amendment.

10.2	KEY SECONDARY EFFICACY PARAMETERS	The gatekeeping testing procedure was replaced by the graphical testing procedure to adjust for multiple comparisons in the primary and secondary efficacy parameters for both rapastinel doses versus placebo.

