11.3	VITAL SIGNS	The orthostatic hypotension was specified to be summarized for pre-dose, post-dose and other visits without IP administration separately for the DBTP.
13.0	INTERIM ANALYSIS	The blinded sample-size re-estimation was replaced by an unblinded interim analysis in order to identify early signs of futility.
14.0	DETERMINATION OF SAMPLE SIZE	The sample size estimation was revised to reflect a reduced significance level (from 0.05% to 0.049%) and associated power for the final primary efficacy analyses due to the addition of interim analysis.

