10.1 PRIMARY EFFICACY PARAMETER

The primary efficacy parameter will be the change from baseline in MADRS total score at the end of treatment (end of Week 6). The MADRS contains 10 items that assess depression, with scores for each item ranging from 0 (absence of symptoms) to 6 (symptoms of maximum severity). The MADRS total score is the sum of the 10 individual items. If more than 2 items are missing, the total score will be set to missing. If there are multiple assessments of MADRS total score for the same day visit of a patient, only the last assessment will be used in the analysis.

The primary parameter will be analyzed using a mixed model for repeated measures (MMRM) with terms for treatment, pooled study center, visit (Day 1 visit and the weekly visits from Week 1 to Week 6), baseline, and treatment-by-visit and baseline-by-visit interactions. An unstructured covariance matrix will be used to model the covariance of within-patient scores. The Kenward-Roger approximation will be used to estimate denominator degrees of freedom (Kenward et al, 1997). This analysis will only use the observed postbaseline scores without imputation of missing values. The treatment differences for rapastinel 450 mg versus placebo and rapastinel 900 mg versus placebo will be estimated and reported along with the corresponding 95% CIs and p-values.

In the case that the MMRM model with unstructured covariance fails to converge with the default algorithm, then the Fisher scoring algorithm will be used to provide better initial values of the covariance parameters; if the model still does not converge, a simplified model without the factor of the pooled study center will be used to find the initial values of the covariance parameters. In the rare event that model still does not converge after using those initial values, simplified covariance structures will be used to fit the model in the following order until the model converges: (1) ante-dependence, (2) heterogeneous autoregressive, (3) Toeplitz, and (4) compound symmetry.

To assess the robustness of the primary MMRM results to the possible violation of the missing-at-random assumption, a sensitivity analysis will be conducted.

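### Does Section 14.0 overstate power by tying 91% per dose to 4.9% when Section 10.2 starts each dose at 2.45%?

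*SAP*

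**What the plan says.** Section 14.0 assumes an SD of 10 points, a within-patient correlation of 0.6 and 20% dropout over 6 weeks. It states that "a sample size of 230 patients per treatment group will provide 91% power to detect a difference of 3.5 points for each rapastinel dose". The comparator is the placebo arm, and the level attached to this power is worded as follows: "at a 2-sided significance level of 4.9% originally adjusting for multiple comparisons of 2 rapastinel groups with placebo". The sentence then goes on to both endpoints, primary and secondary, and names the graphical testing procedure as the tool of adjustment.

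Three other places bear on the 4.9%:

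- Section 13.0 uses a Bonferroni rule to "split the overall Type I Error between the interim and final analysis", giving 0.001 and 0.049.
- Section 3.0 describes the revision of Section 14.0 as "a reduced significance level (from 0.05% to 0.049%) and associated power for the final primary efficacy analyses due to the addition of interim analysis". The percent signs there are a slip for 0.05 and 0.049.
- Section 10.2 says the graph "will be employed to control the overall familywise error rate at" 0.049. On the first step it reads "Specifically, H_1 and H_2 will be tested at" 0.0245 each. A dose that misses 0.0245 at Week 6 is retested at 0.049 only if the other dose has been rejected at both Week 6 and Day 1.

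**The concern.** Taken alone, the words around 4.9% seem to say that this level already allows for comparing two doses with placebo. It does not: the interim split accounts for the whole reduction from 5%, and the dose adjustment is the further halving in Section 10.2. Because the power is quoted per dose, a reader may take 91% as the power of a single Week 6 test at 4.9%, which is not the first test planned for either dose.

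If the sponsor had computed power that way, the figure would be optimistic for a dose that must succeed on its own. With a true 3.5-point effect, some trials give a Week 6 p-value between 0.0245 and 0.049. Section 14.0 read this way counts them as successes. Section 10.2 counts them only if the other dose wins at both time points.

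**Working it through.** **Levels.** 0.001 + 0.049 = 0.05, so the interim split uses up the whole reduction. 0.0245 + 0.0245 = 0.049, so the two-dose split is made inside the graph. The two-sided critical values are 1.9686 at 0.049 and 2.2492 at 0.0245.

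**The plan's figure by the simplest route.** Inputs from Section 14.0: 230 per arm, 20% dropout, difference 3.5, SD 10. Counting completers only, n = 230 × 0.8 = 184 per arm. The standard error is 10 × √(2/184) = 1.0426, and 3.5/1.0426 = 3.357.

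- At 0.049: Φ(3.357 − 1.9686) = 91.75%.
- At 0.0245: Φ(3.357 − 2.2492) = 86.6%.

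The first value is close to 91% but rounds to 92%. This route also leaves the stated correlation of 0.6 unused.

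**With the repeated-measures model of Section 10.1.** There are seven post-baseline visits (Day 1 and Weeks 1 to 6) and monotone dropout reaching 20% by Week 6. Section 14.0 names neither the covariance structure nor the timing of dropout, so both are assumed here. Early means all losses straight after Day 1; even means spread equally; late means all just before Week 6. The Week 6 variance per arm is the last diagonal element of the inverse of the information summed over dropout patterns. Effective n is 100 divided by that variance. Power is Φ(3.5/(10√(2/n)) − c), with n the effective n and c the critical value.

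| Correlation 0.6 | Dropout | Effective n per arm | Power at 0.049 | First test at 0.0245 | Difference (points) |
|---|---|---|---|---|---|
| Exchangeable | early | 198.3 | 93.5% | 89.2% | 4.4 |
| Exchangeable | even | 203.9 | 94.1% | 90.0% | 4.1 |
| Exchangeable | late | 206.3 | 94.4% | 90.4% | 4.0 |
| AR(1) | early | 184.1 | 91.8% | 86.6% | 5.1 |
| AR(1) | even | 188.1 | 92.3% | 87.4% | 4.9 |
| AR(1) | late | 198.3 | 93.5% | 89.2% | 4.4 |

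The last column is the chance that a dose with a true 3.5-point effect has a Week 6 p-value between the two levels.

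**The whole graph.** Section 10.2 was simulated with three arms (at least one million runs), a 3.5-point effect at Week 6 in both doses and the same assumed Day 1 effect in both. The joint Day 1 and Week 6 covariance came from the same model. A dose succeeds if it passes at 0.0245, or if it passes at 0.049 after the other dose has been rejected at both Week 6 and Day 1.

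- Exchangeable, even dropout: 90.6%, 91.2% and 91.9% for Day 1 effects of 1.5, 2 and 2.5 points.
- Day 1 effect needed for 91.0%: about 2.4, 1.9 and 1.6 points (exchangeable; early, even, late) and 2.3 points (AR(1), late).
- However large the Day 1 effect, AR(1) reaches at most 90.9% with even dropout and 90.3% with early dropout.

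So 91% lies above every first-test value and below every single-test value at 0.049 in the table. The whole graph reaches it in four of the six patterns.

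**The case for a change.** The strongest case for a change is this. The power is claimed for each dose, the level attached to it is the familywise one, and the clause next to it credits that level with an adjustment made elsewhere. Even on the kinder reading the sentence is incomplete: per-dose power under the graph depends on the Day 1 effect, because a dose that misses 0.0245 can gain alpha only through the other dose's Day 1 test, and Section 14.0 gives no such effect. The completer calculation at 0.049 comes within a point of 91%, so an unadjusted calculation cannot be ruled out. Readers will use this figure to judge a negative or one-dose result, and a clarifying clause would cost almost nothing.

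Part of this stands. The 4.9% contains no two-dose correction, and the sentence does not say whether 91% belongs to a dose's first test or to the graph.

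The step from there to an error does not stand. The clause does not present 4.9% as the correction; it goes on to name the graph as what adjusts, which is how Section 10.2 uses 0.049. The Day 1 effect, covariance structure and dropout timing behind a power figure are commonly left to the protocol, which is not shown here, so their absence is not a fault of the SAP.

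**Conclusion.** No change is needed. Section 14.0 is loosely worded, but read to its end it fits Sections 10.2 and 13.0: 4.9% is the familywise level left for the final analysis, and the graph divides it between the doses. The rule an analyst must apply is set out in full in Section 10.2, so no one could run a test at the wrong level because of Section 14.0.

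The most that turns on the ambiguity is the gap between a first test at 0.0245 and a single test at 0.049, which is 4.0 to 5.1 percentage points of per-dose power. Measured against the stated 91%, the first-test power is lower by 0.6 points (90.4%) to 4.4 points (86.6%). The graph recovers some or all of that, depending on the Day 1 effect. These figures rest on the assumed covariance and dropout patterns and on equal effects in both doses. The SAP does not show which calculation the sponsor used, so 91% is neither confirmed nor refuted. Labelling the level and the type of power would only record detail in a planning statement. It would leave the tests, alpha levels, sample size and conclusions as they are.
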